8.0 EU-1 Page: 66 of 117 Version

9.1.1 B - Adverse event collection and reporting

All AEs occurring after signature of the study IC and until the EOS are recorded in the eCRF according to the definitions and classifications described under Section 17.2.1. All AEs must be recorded and reported, including AEs that occur during the administration of other drugs. Even if the subject has not yet received the study drug, untoward medical occurrences shall be treated as AEs. After the EOS contact, there is no requirement to actively collect AEs, including deaths.

All laboratory results and vital signs are to be evaluated by the Investigator for clinical significance. Isolated abnormal laboratory results or vital signs findings that are not part of a diagnosis and are considered clinically significant shall be reported as AEs. Medical conditions (including laboratory values/vital signs that are out of range) that were diagnosed or known to exist prior to IC are recorded as medical history.

Adverse events may be directly observed, reported spontaneously by the subject, or reported by the subjects after being questioned by study staff. Holter, ECG and Event Recorder reports may also be used as source to identify AEs. Subjects shall be questioned in a general way, without asking about the occurrence of any specific symptoms. The Investigator must assess all AEs to determine seriousness, severity, and causality, in accordance with the definitions in Section 17.2.1. The Investigator's assessment must be clearly documented in the site's source documentation with the Investigator's signature.

All SAEs recorded on the AE eCRF page, that meet seriousness criteria (see Section 17.2.1.2) or that meet the criteria for AESI (serious or non-serious; see Section 9.1.2 B) must be reported within 24 hours of the Investigator's awareness. If all the required information is not available, the information which is available is to be recorded without delay (within 24 hours), and the outstanding data recorded as soon as available thereafter. Responses to queries related to the reported SAE or AESI must be provided as soon as possible.

In case of an occurrence of an AE, the Investigator must ensure appropriate medical treatment and shall decide whether to discontinue or interrupt the study drug, as applicable.

For each SAE, a separate assessment for expectedness, seriousness, and causal relationship to study drug is performed by the Sponsor in addition to the assessment from the Investigator.

The Investigator is responsible for continuous monitoring of all SAEs (whether or not related to study drug) until resolution or until the event is considered chronic and/or stable by the Investigator and/or other physician who has the responsibility for the subject's medical care. Follow-up SAE reports are reported according to the same timelines as initial reports, as soon

INSTANT Study Clinical Study Protocol

Study no. FLE-002

Version 8.0 EU-1 Page: 67 of 117

as new significant information becomes available and within 24 hours of the Investigator's awareness of the event.

For all EU subjects who consent to the Part C Patient-Led Under Medical Supervision Cardioversion Study, AEs will continue to be collected until the subject withdraws or is withdrawn, or until EOS (Day 5 after treatment for a recurrent episode of AF or 8 months after signing informed consent for the Part C Patient-Led Under Medical Supervision Cardioversion Study, whichever comes first).

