Enrollment (study drug allocation) occurs on Day 1 (day of dosing) and the start of the first inhalation is time zero (T_0) .

An overview of study assessments is shown in Figure 4. Vital signs, triplicate 12-lead ECGs, and blood samples for PK analysis are collected at multiple serial time points just before, during, and after the inhalation regimen, and at the time of conversion of AF to SR as detailed in the Schedule of Assessments. AECG (12-lead Holter) data are collected from 45 minutes pre-dose until 90 minutes post dose in order to identify the time of conversion of AF to SR and to monitor the safety of the study subjects. Time to discharge of the subject is left to the discretion of the treating physician but may not be scheduled prior to 90 minutes post dose (a — (minus) 10-minute window is allowed).

If conversion of AF to SR does not occur within 90 minutes post dose, the Investigator may offer another appropriate therapy, as per institutional standard, except for IV ibutilide, procainamide, or sotalol which are not allowed. See Section 5.4.2 B for specific requirements.

All subjects have a Day 2 (+1 day) and a Day 5 (± 1 day) telephone assessment (Visit 1 and Visit 2, respectively). ECG recordings are also obtained by the subject on Day 2 and Day 5 using an Event Recorder. All enrolled subjects are followed for 5 days and every effort shall be made to maintain the scheduled follow-up of the subject. End-of-study activities are completed for all enrolled subjects who received study drug. Study follow-up is only terminated at the explicit

INSTANT Study

Clinical Study Protocol

[figure not shown]
Study no. FLE-002

Version

8.0 EU-1 Page: 42 of 117

request of the subject. The overall duration of subject participation from screening through follow-up is 5 days.

Figure 4. Study assessments diagram Part B

- · AF monitoring must continue for at least 45 minutes prior to study drug administration regardless of enrollment time.
- Definitions: AF- atrial fibrillation; AECG- ambulatory ECG; min.- minutes; EOS- end-of-study; IC- informed consent.

The study organization is described in Section 17.3. An independent DSMB periodically reviews pertinent study data to protect the safety of the subjects participating in the study.

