9.1.2.2 B - Pregnancies

Any female study subject or female partner of a study subject that becomes pregnant while participating in this study must be reported within 24 hours of the Investigator's awareness. All pregnancies must be followed to conclusion to determine their outcome. This information is important for both drug safety and public health concerns. The Investigator shall contact the Medical Monitor to discuss subject management.

9.1.2.3 B - AEs known to be related to other flecainide formulations (i.e., IV and oral)

The following events are known to be related to other formulations of flecainide (i.e., IV and oral) and are considered AESI if they occur after the initiation of study drug. These events will be monitored closely and will be followed to conclusion to determine their outcome.

- Hypotension: an acute hypotensive episode (AHE) is a sudden drop in BP resulting in a BP < 90/60 mmHg (MAP < 70 mmHg) that lasts for at least 5 minutes and is based on multiple sequential readings (≥ 3). MAP is calculated as 1/3 (SBP – DBP) + DBP.
- Ventricular tachycardia ≥ 3 beats
- Bradycardia: an ECG-derived rate < 50 bpm for ≥ 1 minute
- Sinus pause post conversion of AF to SR: an ECG-derived pause > 3 seconds
- Atrial flutter with 1:1 conduction with fast ventricular response (ventricular heart rate ≥ 200 bpm)

INSTANT Study Clinical Study Protocol

Study no. FLE-002

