**5.2 Rhythm monitoring assessment (Holter)**

The Holter analysis is performed by a Core Laboratory. Heart rhythm information is provided in two SAS datasets to the statistical department of Cardialysis. The first dataset shows summary data for the complete monitoring period, including if subject converted to SR during the Holter recording and if so: time of conversion and if recurrence of AF was observed. If recurrence of AF was observed the time of first recurrence of AF is indicated.

The second dataset shows details for separate phases in the recording being:

- If a subject converted to SR: Pre-Dose, start of dosing to time of conversion, time of conversion to End of Recording
- If a subject did not convert to SR: Pre-Dose, Dosing, Post-Dose

Information is available for Part A, Part B and Part C MLS subjects and for Part C PLS subjects.

Additionally, in Part A, Part B and Part C MLS Heart Rates (BPM) recorded for each rhythm strip within the Holter Report are entered by the Core Laboratory directly into the EDC, as these data cannot be provided within the SAS datasets. In the Part C PLS, the Heart Rate data from the rhythm strips was not collected in the EDC.

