### 5.8 Protocol Deviations

Protocol Deviations are registered in the CTMS system. After eCRF database lock and after approval by InCarda, the final listing of Protocol Deviations will be provided to STAT in the form of an Excel file. This file will include: an indicator if Protocol Deviation is major or minor, and the type of Protocol Deviation (e.g. ECGs).

Information is available for Part A, Part B, Part C MLS subjects and for Part C PLS subjects.

**FLE-002 (INSTANT) – Final Analysis****Statistical Analysis Plan****6 Study Endpoints: definition and availability of information**

The final report will be in line with the final statistical report for Part B, reporting all endpoints that were included in the final report of Part B of the trial. As in the Part B report all Part A and Part B subjects receiving 2\*60 mg FlecIH-103 are included in the analysis, in the final report these subjects are pooled with the Part C MLS subjects. Sections 6.1 to 6.2.5 describe these study endpoints as defined in version 8.0/EU-1 of the protocol. Section 6.2.6 describes the additional exploratory endpoints for the Part C PLS.

For the endpoints *Conversion from AF to SR* and *Recurrence of AF*, in principle, only Core Laboratory information will be used, this applies for the Holter and TTM AF monitoring period.

In Core Laboratory results, Conversion of AF to SR is reported by filling out column SRTM (Date and Time Rhythm Switched to SR). In the statistical analysis then is reported: Subject did convert, time of conversion is the Date and Time shown in SRTM. Refer to section 3.1. of the SAP for the definition of Conversion (Rhythm Switch) to SR. If data in the column SRTM is missing, subject did not convert during the period analyzed by the Core Laboratory.

For subjects who converted from AF to SR, the column AFIBAFTER (Atrial Fibrillation Recurrence Post-Rhythm Change) indicates if AF recurred (value: "YES") or did not recur (value: "NO"). If AF did recur, column AFIBRTM (Atrial Fibrillation Recurrence Time) shows the Date/time of the first AF recurrence.

Investigator reported information on conversion and recurrence of AF is also reported for the 90 minutes after the end of dosing. This information will not be used in the statistical analysis unless Core Laboratory information is Completely Missing (no analysis at all) or Partly Missing (e.g., analyzed only up to only 28 minutes of the planned 90 minutes post dose).

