## FLE-002 (INSTANT) – Final Analysis

## Statistical Analysis Plan

---

5.2.2 Each AE will be reviewed, and documented as follows:

- AE type (select only one option)
  - Non-AESI (standard AE)
  - Non-CV Non-Serious AESI
  - Serious Non-CV AESI
  - CV Non-Serious AESI
  - Serious CV AESI
- Initials
- Date
- Comment

5.2.3 The Reviewer initials and dates next to each recoded item and provides comments as necessary.

5.2.4 The Reviewer also signs a memorandum to record execution.

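### AESI tables rest on adverse events that sites entered, and no stated step compares Core Laboratory Holter findings with that listing, so brief rhythm AESIs may be under-ascertained

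*Protocol*

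**What the plan says.** **Definitions.** Protocol 9.1.2.3 B lists five flecainide AESIs. One is hypotension. The other four are rhythm findings: VT of 3 beats or more; a heart rate on ECG below 50 bpm that persists for a minute or longer; 1:1 atrial flutter with the ventricles at 200 bpm or faster; and, quoted here as an example of the form, "Sinus pause post conversion of AF to SR: an ECG-derived pause > 3 seconds". For tabulation, SAP Annex A 4.5 narrows the VT item to more than 3 beats, with triplets excluded.

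**Recording.** Protocol 3 B gives the Holter two purposes, to time the conversion and "to monitor the safety of the study subjects". Protocol 7.1 B has recordings analysed centrally. SAP 5.2 describes a summary dataset (conversion, AF recurrence) and a dataset by recording phase, and adds that "Heart Rates (BPM) recorded for each rhythm strip within the Holter Report are entered by the Core Laboratory directly into the EDC".

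**Finding and reporting events.** Protocol 9.1.1 B requires all AEs to be recorded, and AESIs to be reported within 24 hours of the investigator learning of them. On the Holter it says only that "Holter, ECG and Event Recorder reports may also be used as source to identify AEs".

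**Tables.** For Parts B and C MLS, SAP 5.6.3 makes the clinical AE database the sole source of the AE tables and reconciles it with the pharmacovigilance database. Part A uses the CRO safety database (SAP 5.6.4). The sponsor's AESI review (SAP 5.6.5 and Annex A) starts from a coded listing of reported AEs: "Each AE will be reviewed, and documented as follows", with one category assigned to each.

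**Efficacy, for comparison.** For conversion and AF recurrence, SAP section 6 states that "in principle, only Core Laboratory information will be used"; investigator data are used where the Core Laboratory reading is missing or partial.

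**The concern.** The same recording is treated in two ways. For efficacy, the central reading takes precedence over the site. For safety events defined by an ECG threshold, the site's entry decides, and neither document sets the central reading against it.

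A three-second pause or a short run of VT can meet the AESI definition without symptoms and without being noticed at the bedside. Protocol 9.1.1 B has subjects questioned in general terms, which is unlikely to reveal silent events. A missed event lowers the count, nothing in this step raises it, and in a single-arm study no comparator cancels the loss.

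Annex A was written because AESI definitions and collection differed between Parts A, B and C. It makes classification uniform but leaves detection as it was in each part, so the pooled AESI rate may still partly reflect how sites looked for events.

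**Working it through.** The documents give no AESI rate and no detection sensitivity, so there is no plan figure to reproduce. The check has three steps: follow an event from definition to table, see where an unreported event could re-enter, and illustrate the size.

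**1. Can an unreported qualifying event reach the AESI table?**

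- *Definition (Protocol 9.1.2.3 B):* a pause over 3 seconds qualifies with no symptom.
- *Detection (Protocol 9.1.1 B):* telemetry may show it; searching the Holter is permitted, not required.
- *Reporting duty (Protocol 9.1.1 B and 9.1.2 B):* mandatory, but triggered by awareness. An event nobody saw creates no duty.
- *Reconciliation (SAP 5.6.3):* against the pharmacovigilance database. No Holter input to that database is described.
- *Sponsor review (SAP 5.6.5; Annex A 2.1, 5.1, 5.2.2):* input is the AE listing, output is one category per AE. It can move an AE into or out of AESI but has no step that creates one.
- *Holter datasets (SAP 5.2):* described for conversion, recurrence and recording phases. No step derives AESIs from them.
- *PD listings (SAP 6.2.5.2, 9.2.2.11):* heart rate from triplicate ECGs at scheduled times, averaged per time point. These may show a sustained slow rate, but a pause or short VT run between time points would not appear.

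On the stated plan, such an event has no route into the AESI table.

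**2. Which counts are exposed?** The AESI tables are. For SAESI (Protocol 9.1.2.4 B; Annex A 4.6), bradycardia needs clinical instability and pacing or a chronotropic agent; a pause needs syncope, pacing or CPR; 1:1 flutter needs an intervention. Sustained VT, over 30 seconds, is the main criterion that rhythm alone can meet.

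The Holter also limits what a cross-check can see. Dosing takes 3.5 + 1 + 3.5 = 8 minutes, and recording continues to 90 minutes after dosing, so a full recording covers about 8 + 90 = 98 minutes from T0. Treatment-emergent events run to Day 5.

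**3. Illustration of size.** Assumed N = 54: 29 Part A FlecIH-103 subjects (Protocol 1.4) plus about 25 in Part B. The Part C MLS number is not given and would raise N. Let p be the true proportion of subjects with a qualifying rhythm event, and s the share of them with such an event on the AE page. Expected observed incidence = p × s; expected subjects = 54 × p × s. Both p and s are assumptions.

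- p = 10% (54 × 0.10 = 5.4 subjects): s = 90%, 70%, 50% gives 9.0%, 7.0%, 5.0%, or 4.9, 3.8, 2.7 subjects.
- p = 20% (54 × 0.20 = 10.8 subjects): the same shares give 18%, 14%, 10%, or 9.7, 7.6, 5.4 subjects.

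Exact (Clopper-Pearson) 95% intervals show whether such a loss would be visible:

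- 4/54 = 7.4% (2.1% to 17.9%)
- 8/54 = 14.8% (6.6% to 27.1%)

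The intervals overlap widely, so if 8 subjects had an event and only 4 were reported, the AE data alone would not reveal it.

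**The case against.** Much of the opposing case stands. Reporting is mandatory once the investigator knows of an event, so a reader who infers that sites choose which AESIs to report would be wrong; the discretion lies in whether the Holter is searched. Subjects are on continuous telemetry throughout Day 1 (Protocol 6.2.1 B), and Holter-extracted ECGs are provided to investigators (Protocol 8.2 B). In Part A, sites did report minor, transient bradycardia and a sinus pause graded mild (Protocol 1.4).

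A reader might also infer that every subject has a complete central reading. The Holter is planned for all, but SAP section 6 provides for readings that are wholly or partly missing.

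A Holter-to-AE reconciliation may exist in the Core Laboratory analysis plan or the Safety Management Plan. Both are cited in the protocol, and neither is available here. The supportable statement is that the protocol and SAP do not describe one.

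Finally, SAP 5.2 does not say that the Holter datasets hold pause lengths or VT run lengths, so a complete derivation might need a re-read. AESI counts are descriptive, with no test or decision attached.

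These points limit the claim and shape the remedy. They do not close the gap: telemetry reduces the chance of a missed event, but nothing stated in the plan would show whether one was missed.

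**Conclusion.** The point holds as a risk of under-ascertainment with a known direction and an unknown size. Followed as written, the plan can leave threshold-meeting rhythm events out of the AESI tables, and any such omission lowers AESI incidence.

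Two stronger conclusions are tempting and not supported. One is that AESI incidence is in fact biased downward: the documents show no missed event, and the figures above rest on assumed values of p and s and an assumed N of 54. The other is that the secondary safety endpoint is undermined: apart from sustained VT, most SAESI criteria need symptoms or an intervention that would be hard to overlook under monitoring.

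The conclusion assumes that no reconciliation is set out in the Core Laboratory analysis plan or Safety Management Plan. If one is, the remaining gap is a missing cross-reference in the SAP. The change is worth making as a cheap improvement to a single-arm safety summary.

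**What to change.** Amend SAP 5.6.5, 9.2.2.9 and Annex A 5.1 as follows.

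- Before lock, compare the existing Core Laboratory Holter reports, from T0 to the end of recording, with the AE listing for the four rhythm AESIs. Use the Annex A 4.5 definitions (VT of more than 3 beats, triplets excluded) so that Holter-based and AE-based columns are comparable.
- Query each qualifying Holter event without a matching AE where the database is still open. SAP 5.6.3 calls Part B final, and SAP 5.6.4 keeps Part A results as already reported, so for those parts the Holter count stands beside the AE count without changing it.
- Tabulate by cohort the subjects with at least one qualifying Holter event beside the AE-based AESI count. The denominator is subjects with an evaluable Holter; state how many readings are missing or partial, so that an absent recording is not counted as no event.
- Limit this to event types that the existing Core Laboratory output records, and name any that it does not capture.
- If a reconciliation already exists in the Core Laboratory analysis plan or Safety Management Plan, cite it.

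Rewording Protocol 9.1.1 B would not repair data already collected: Part C MLS enrolment stopped on 31 December 2021, and SAP V5.0 is dated 6 July 2022.

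The cost is one comparison, one table and some queries. The downside is that some minor asymptomatic events are counted and the AESI figure may look less favourable.

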9.1.2 B - Events of special interest

The following AESIs (even if classified as non-serious) will be reported within 24 hours of the Investigator's awareness by recording them on the AE page of the eCRF.

9.1.2.1 B – AEs related to inhalation device

Events related to the inhalation device (AeroEclipse® II BAN) are considered AESI. All AEs related to inhalation device are followed to conclusion to determine their outcome. Inhalation devices associated with AESIs are to be retained and returned to the Sponsor for further evaluation as appropriate.

9.1.2.2 B - Pregnancies

Any female study subject or female partner of a study subject that becomes pregnant while participating in this study must be reported within 24 hours of the Investigator's awareness. All pregnancies must be followed to conclusion to determine their outcome. This information is important for both drug safety and public health concerns. The Investigator shall contact the Medical Monitor to discuss subject management.

9.1.2.3 B - AEs known to be related to other flecainide formulations (i.e., IV and oral)

The following events are known to be related to other formulations of flecainide (i.e., IV and oral) and are considered AESI if they occur after the initiation of study drug. These events will be monitored closely and will be followed to conclusion to determine their outcome.

- Hypotension: an acute hypotensive episode (AHE) is a sudden drop in BP resulting in a BP < 90/60 mmHg (MAP < 70 mmHg) that lasts for at least 5 minutes and is based on multiple sequential readings (≥ 3). MAP is calculated as 1/3 (SBP – DBP) + DBP.
- Ventricular tachycardia ≥ 3 beats
- Bradycardia: an ECG-derived rate < 50 bpm for ≥ 1 minute
- Sinus pause post conversion of AF to SR: an ECG-derived pause > 3 seconds
- Atrial flutter with 1:1 conduction with fast ventricular response (ventricular heart rate ≥ 200 bpm)

INSTANT Study Clinical Study Protocol

Study no. FLE-002

8.0 EU-1 Page: 68 of 117 Version

9.1.2.4 B – Serious Adverse Events of Special Interest (SAESI)

The following potential SAESIs are defined for study purposes:

- Hypotension, with symptoms/signs of clinical instability (i.e., severe chest pain/dyspnea or altered mental status), and requiring a vasopressor or inotropic agent
- Ventricular tachycardia, sustained (> 30 seconds or requiring intervention before that time) VT, TdP, or VF
- Bradycardia, with symptoms/signs of clinical instability (i.e., severe chest pain/dyspnea, altered mental status or hypotension), and requiring pacing or a chronotropic agent
- Sinus pauses post conversion of AF to SR, causing syncope, or requiring pacing or CPR
- Atrial flutter with 1:1 conduction with fast ventricular response (ventricular heart rate ≥ 200 bpm), and requiring intervention (DC cardioversion) for termination, or an IV AV nodal blocking agent (β-blocker or Ca2+-channel blocker) to slow the ventricular rate
- Any arrhythmia with symptoms/signs of clinical instability (i.e., severe chest pain/dyspnea, altered mental status or hypotension), and requiring DC cardioversion, defibrillation, pacing, or a vasopressor, inotropic or chronotropic agent

